- c) Surveys should occur within approximately 4 weeks of the last patient study participant visit at each site and interviews of staff study participants should occur after at least 50% of Month 12 patient study participant visits at each site.

All patient study participants enrolled in this study will switch from their pre-entry oral HAART regimen to the CAB + RPV LA regimen (single arm switch study) for at least 12 months, including a one-month safety lead-in period with oral cabotegravir and oral rilpivirine (Edurant) dosed once-daily. Patients who successfully complete the Month 12 visit and assessments will have completed the study and will need to obtain ongoing HIV treatment outside of the study. Patients who discontinue the CAB + RPV LA regimen after receiving ≥ 1 injection of cabotegravir and/or rilpivirine will enter a long-term

follow-up period with safety and efficacy/virology evaluated on a quarterly basis for 1 year.

Site/Clinic Selection: Investigational sites that have not previously delivered the CAB + RPV LA regimen will be targeted for inclusion in the study and screened based upon objective criteria of their ability to perform the assessments required in the study within GCP requirements. Sites will be identified as either university/hospital, private or public health clinic based upon their own determination (Principal Investigator determination). Clinics that include participants from multiple categories (public/private) will be categorized based on the principal investigator's determination of the majority of their patient base. In order to create a representative sample, sites will be chosen not only to represent all three categories of clinic type, but also based upon geographic and demographic representation (rural, suburban, urban), as much as possible within practical limitations.

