Safety and efficacy assessments will be conducted as per the Schedule of Assessments. Dosing will occur according to the selected regimen.

If the intramuscular (IM) dosing regimen is discontinued as a result of an independent data monitoring committee (IDMC) review from the ongoing Phase 3 studies, any subsequent analysis, or any other programmatic analysis, those participants who have not met any clinical management criteria for discontinuation will be discontinued permanently from the study and will enter into the LTFU Phase of the study.

LTFU Phase –Following the IM Regimen Only

Any participant who receives *at least one* dose of CAB LA and/or RPV LA and discontinues the CAB LA + RPV LA regimen for any reason must remain on suppressive HAART for at least 52 weeks after the last dose of CAB LA and/or RPV LA in order to prevent selective pressure on HIV during the period of declining drug exposures and the potential for selection of resistant mutants. **Investigators must discuss the choice of the follow-up HAART regimen with the Medical Monitor prior to initiating the new regimen with the participant. HAART therapy should be initiated within 4 weeks after the last monthly injection, however if withdrawn due to virologic failure, HAART should be initiated as soon as virologic failure is confirmed. Discuss with medical monitor.** The Long-Term Follow Up period (LTFU) will begin the day of the last CAB LA and/or RPV LA dose and continue for 52 weeks. These participants will not complete a Withdrawal visit, but will instead move directly into the LTFU as per the Schedule of Activities, Section 1.5. In addition, for participants who withdraw during the LTFU, the final visit will be considered the study withdrawal visit.

Participants will be assessed with clinic visits at months 3, 6, 9, and 12 during the LTFU Phase. Female participants of child bearing potential must continue to use adequate contraception methods for the entire year of follow up.

In order to assure that participants have access to HAART during the LTFU, ViiV Healthcare may supply HAART or reimbursement may be provided as needed during this phase. The LTFU Phase may be shortened or terminated at any time during the study for various reasons, e.g., better understanding of risks of development of resistance as CAB and RPV exposures decline, end of study timings, etc.

Staff study participants

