Patient Questionnaire			X			X								X	
Selected Patient Interviews (SSI) ^m		X												X	

See footnote "c" for continuation of visit schedule after Month 12, if required. Subjects will continue on study until the CAB + RPV LA regimen is either locally approved and commercially available, the participant no longer derives clinical benefit or meets a protocol-defined reason for discontinuation or until development is terminated.

- A screening visit will be conducted within 21 days of Day 1. However, it is preferred for Day 1 to be conducted as soon as practical after all screening results are available.
- After discussion of risk:benefit, a pregnancy specific ICF addendum must be signed by pregnant participants who wish to remain in the study
- Continue this pattern for visits for the remainder of the study if needed, until commercial CAB + RPV LA is available. For example, Month 13 will be conducted as per Month 10, Month 14 will be conducted as per Month 11, Month 15 will be conducted as per Month 12, Month 16 will be conducted as per Month 10, and so on. The exception to this pattern is that no questionnaires, study visit length collection, or patient interviews will be conducted after the Month 12 visit.
- Physical exams should be conducted as part of normal routine clinical care but data will not be collected in the electronic case report form (eCRF). Medical assessments include any decisions the study staff must make for participant management.
- Measure vital signs after about 5 minutes of rest in a semi-supine position.

- f. Height collected at Day 1 only.
- g. At Screening, ECGs should be performed in triplicate at least 5 minutes apart and following 5 minutes of rest in a semi-supine position. ECG evaluations performed at subsequent visits should be obtained after dosing, preferably 2-4 hours post dosing. ECG at Withdrawal should be performed following 5 minutes of rest in a semi-supine position.

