4.4. End of Study Definition

4.4.1. Study Completion

Patient Study Participants

The investigator is responsible for ensuring that consideration has been given to the post-study care of the patient study participant's medical condition.

Patient study participants are considered to have completed the study if they remain on therapy (i.e., have not permanently discontinued study intervention) and satisfy the following:

- Have completed all Month 12 evaluations
- remaining on study until commercial supplies of the CAB LA + RPV LA regimen becomes locally available, or initiates alternate antiretroviral therapy at the discretion of their HIV care provider, or
- development of CAB LA + RPV LA is terminated;

Upon completion of the above, patient study participants will exit the study and transition to commercial supplies of CAB LA + RPV LA, or alternate antiretroviral therapy at the discretion of their HIV HCP.

Until meeting the definition for study completion, participants will continue in the study until:

- the participant no longer derives clinical benefit,
- the participant meets a protocol-defined reason for discontinuation

Participants who withdraw from CAB LA + RPV LA and go into the LTFU Phase will be considered to have prematurely withdrawn from the study intervention.

Patient study participants will complete the 52-week Follow-Up phase required for participants who receive one or more injections with CAB LA or RPV LA. Assessments at the Follow-up visits should reflect any ongoing complaints (e.g., blood draws to follow a laboratory abnormality). Follow-Up visits are not required for successful completion of the study.

Study Staff Participants

Study Staff participants will have completed the study upon completion of all surveys and qualitative interviews after Month 12 evaluations have been completed at their site, per the Schedule of Activities (Section 1.5).

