6.7. Intervention after the End of the Study

The investigator is responsible for ensuring that consideration has been given to the post-study care of the participant's medical condition, whether or not GSK is providing specific post-study intervention. Participants who have successfully completed IM dosing for 12 months will continue to have access to both CAB LA and RPV LA until study intervention is either locally approved and commercially available, the participant no longer derives clinical benefit, the participant meets a protocol-defined reason for discontinuation or until development of either CAB LA or RPV LA is terminated.

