7.1.4.3. Confirmed Virologic Failure

Participants with CVF must be discontinued from study treatment. However, participants who have received at least one dose of CAB LA or RPV LA prior to confirming virologic failure will remain in the study on oral HAART in the LTFU Phase.

A plasma sample from the suspected virologic failure visit as well as Day 1 (if baseline HIV-1 RNA level ≥ 200 c/mL) will be sent for genotypic and phenotypic resistance testing and the result made known to the Investigator when available. A plasma sample from the confirmation visit will be obtained for storage. This sample may be used for possible future analyses, e.g., for genotypic and phenotypic analyses of participants who experience virologic failure.

For all participants who meet CVF, baseline and suspected virologic failure plasma samples with HIV-1 RNA level ≥ 200 c/mL will be analyzed in an attempt to obtain genotype/phenotype data on as many samples as possible. Plasma samples for storage will also be obtained at unscheduled visits including confirmation of CVF. Participants may continue to receive study drug at the discretion of the investigator until results of resistance testing are available at which time the participant must be discontinued from the study. Even if genotype/phenotype data cannot be generated, participant must also be discontinued from the study intervention.

If a participant is prematurely discontinued from the study intervention, the investigator must make every effort to perform the Withdrawal Visit evaluations outlined in the Schedule of Activities Table, Section 1.5. These data will be recorded as they comprise essential evaluations needed to be done before discharging any participant from the study.

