10.3.3. VSLC Decision Process for Drug Restart Approval or Disapproval

- Principal Investigator (PI) requests consideration of drug re-initiation for a participant stable or improving on IP, who exhibits liver chemistry elevation meeting participant stopping criteria, which is transient, non-drug-related, and liver chemistries have improved to normal or are within 1.5x baseline and ALT < 5xULN.
- GSK Medical Monitor and GCSP Physician to review the participant's diagnosis restart risk factors (Hepatotoxicity Panel consultation is available) and complete checklist (Table 14).
 - *must present source data defining the patient's current resistance profile with documented evidence of extensive drug resistance and previous drug history.*
- The local operating company (LOC) medical director should be informed that study drug restart is under consideration and of the final decision, whether or not to proceed.
- Relevant physicians (listed below) must review and agree on action to be taken regarding request for drug restart:
- Safety Review Team Leader, Safety Development Leader, or Senior Safety Physician
- MDL and PPL
- Request is taken to VSLC for final decision

Table 14 Checklist for Phase III drug restart after well-explained liver injury (e.g. biliary, pancreatic, hypotensive events, congestive heart failure (CHF), acute viral hepatitis), and improvement of liver chemistry to normal or $\leq 1.5x$ baseline & ALT < 5xULN

	Yes	No
Is participant stable or improving on IP?		
Do not restart if the following risk factors at initial liver injury:		
fever, rash, eosinophilia, or hypersensitivity		
drug-induced liver injury		
alcoholic hepatitis (AST > ALT, typically < 10xULN)		
IP has an HLA genetic marker associated with liver injury (e.g. lapatinib, abacavir, amoxicillin/clavulanate)		
Source data defining the patients current resistance profile		
Previous drug history		

Figure 6 VSLC process for drug restart approval or disapproval

10.3.4. Medical monitor, GCSP Physician and PI actions for Restart or Rechallenge following VSLC decision

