10.6.2. Liver Chemistry Stopping and Follow-up Criteria

Liver chemistry threshold stopping criteria have been designed to assure participant safety and to evaluate liver event etiology during administration of study drug and the follow-up phase (See also Section 10.3, [Appendix 3](#)). All Phase 3 participants who meet liver stopping criteria will be adjudicated by the ViiV Safety and Labelling Committee (VSLC) – resulting in a case summary, adjudication, and management plan. The VSLC contains an external expert hepatologist, familiar with both DILI and cabotegravir, who will participate in this review. This committee meets on a 3-weekly basis, and can be convened on an ad hoc basis as needed.

Drug Restart Following Transient Resolving Liver Events Not Related to Study Drug

Approval by VSLC for drug restart can be considered where:

Liver chemistries have a clear underlying cause (e.g., biliary obstruction, hypotension, and liver chemistries have improved to normal or are within $1.5 \times$ baseline and $ALT < 3 \times ULN$). Ethics Committee or IRB approval of drug restart must be obtained, as required.

If restart of drug is approved by VSLC in writing, the participant must be provided with a clear description of the possible benefits and risks of drug administration, including the possibility of recurrent, more severe liver injury or death.

The participant must also provide signed informed consent specifically for the restart. Documentation of informed consent must be recorded in the study chart.

Study drug must be administered at the dose specified by VSLC.

Participants approved by VSLC for restarting study drug must return to the clinic once a week for liver chemistry tests for a minimum of one month and thereafter for as long as clinically indicated and then laboratory monitoring may resume as per protocol. If protocol defined stopping criteria for liver chemistry elevations are met, study drug must be stopped.

Refer to Section 10.2, Appendix 2, U.S. Department of Health and Human Services, National Institutes of Health, National Institute of Allergy and Infectious Diseases, Division of AIDS. Division of AIDS (DAIDS) Table for Grading the Severity of Adult and Pediatric Adverse Events, Version 2.1. [March 2017]. Available from: <https://rsc.tech-res.com/docs/default-source/safety/daids-ae-grading-table-mar2017.pdf>

Refer to Section 10.3.3: Liver Safety – Study Treatment Restart Guidelines for further details.

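### The protocol gives conflicting rules on study drug after Month 12, on treatment and study status after confirmed virologic failure, and on the ALT limit for restart after a liver event

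*Protocol*

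**What the plan says.** **After Month 12.** Section 1.3 (Overall Design) states that patients who complete the Month 12 visit "will have completed the study and will need to obtain ongoing HIV treatment outside of the study". Further on, under Intervention Groups and Duration, Section 1.3 lists the reasons for ending injections, and reaching Month 12 is not among them. The note under Table 3 in Section 1.5 says "Subjects will continue on study until the CAB + RPV LA regimen is either locally approved and commercially available", or another listed reason applies, and sets a visit pattern from Month 13 onward. The dosing table in Section 6.1 runs to the same end point. Section 6.7 says "Participants who have successfully completed IM dosing for 12 months will continue to have access to both CAB LA and RPV LA" until that point. Section 4.4.1 makes completion of Month 12 one listed item; another is staying until commercial supply, "or initiates alternate antiretroviral therapy at the discretion of their HIV care provider".

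**After confirmed virologic failure (CVF).** Section 7.1.4.3 opens by requiring discontinuation of study treatment. It later adds: "Participants may continue to receive study drug at the discretion of the investigator until results of resistance testing are available". The LTFU part of Section 1.3 says that "if withdrawn due to virologic failure, HAART should be initiated as soon as virologic failure is confirmed". On study status, Section 7.1.4.3 keeps participants with at least one long-acting dose in the study, on oral HAART in LTFU, and later has the participant leave the study once resistance results are in.

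**Restart after a liver event not caused by study drug.** Section 10.3.3 allows a request to the ViiV Safety and Labelling Committee (VSLC) when "liver chemistries have improved to normal or are within 1.5x baseline and ALT < 5xULN"; Table 14 repeats that limit. Section 10.6.2 describes the same VSLC approval with the same 1.5-times-baseline condition but an ALT limit of 3×ULN, and refers to Section 10.3.3 for details.

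**The concern.** Each set of statements covers one decision for one participant and gives incompatible answers. The protocol allows no waivers and calls adherence essential (Sections 1.3 and 6.6), but a site cannot follow both versions.

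The matter is not editorial. Sections 2.3.1 and 6.6.2 warn that drug can persist for more than a year after the last injection, with a risk of resistance as levels fall. The unclear rules decide who is still being injected, who is followed during that tail, and when a failing participant changes treatment. For the data, they decide who counts as a completer and how long safety and virology are observed.

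**Working it through.** No sample-size or power figure is involved. The check sets the passages side by side, with one piece of arithmetic for the ALT limit.

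**1. After Month 12**

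- Version A (Section 1.3, Overall Design): the study ends for the patient at Month 12, and treatment is found elsewhere.
- Version B (Section 1.3, Intervention Groups and Duration; Sections 1.5, 6.1 and 6.7): injections and visits continue until commercial availability or another listed reason.
- If the regimen is not on the market when a patient reaches Month 12, A and B cannot both be followed.
- LTFU: Section 4.4.1 lets a completer move to other therapy. Section 1.3 sends anyone with at least one long-acting dose who stops the regimen, whatever the reason, to 52 weeks of HAART and LTFU. Section 7 sends anyone who stops permanently before commercial availability to LTFU. Section 4.4.1 treats LTFU entrants as premature withdrawals from study intervention, says the 52-week phase will be completed, and says follow-up visits are not needed for study completion.
- A patient who finishes Month 12 and then switches to oral therapy is therefore a completer without LTFU on one reading and an LTFU entrant on another.
- Reach: 9 sites × 15 patients = 135 at most. The number reaching Month 12 is not given.

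**2. After CVF**

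- Treatment: one sentence of Section 7.1.4.3 stops it; a later one lets it continue, at the investigator's discretion, until resistance results.
- If the later sentence is taken as a timing exception, it still disagrees with the HAART timing in Section 1.3.
- Status: for injected participants, Section 7.1.4.3 says both that they stay in the study (LTFU) and that they leave it.
- Reach: any CVF, defined in Section 7.1.3 as two consecutive HIV-1 RNA values of at least 200 c/mL. No expected number is given.

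**3. ALT limit for restart**

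Both sections require chemistries to be normal or within 1.5×baseline, plus an ALT limit L, with L = 5×ULN (Section 10.3.3, Table 14) or L = 3×ULN (Section 10.6.2).

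- ALT below 3×ULN: within both limits.
- ALT of 5×ULN or more: outside both.
- ALT from 3 to below 5×ULN: within the first limit, outside the second.
- In that band ALT is not normal, so the other condition must hold: ALT ≤ 1.5×baseline. With ALT ≥ 3×ULN, baseline ≥ 3/1.5 = 2×ULN.
- A participant with baseline ALT below 2×ULN is ineligible in that band under both sections, so the conflict does not touch that participant.
- Such baselines can occur: exclusion criterion 22 (Section 5.2) removes ALT of 5×ULN or more, or of 3×ULN or more with raised bilirubin, but not an isolated ALT of 2 to below 5×ULN.

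**The case against.** The best case on the other side has four parts.

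- *One stray sentence.* Most sections favour continuation after Month 12, and the paragraph in Section 1.3 itself speaks of at least 12 months. A reader might infer that continuation is meant. That is plausible, but the exit sentence is explicit and current, and a count of sections does not settle the rule. It also leaves LTFU for a completer who stops injections unanswered. Moving to other therapy does not in itself contradict staying on suppressive HAART; the open question is LTFU entry and status.
- *CVF is a rule with a bounded allowance.* Both sentences on treatment end in discontinuation, and the timing of HAART is discussed with the medical monitor (Section 1.3; Table 5, note f). This narrows the treatment conflict to one of timing. It removes neither the disagreement with Section 1.3 nor the contradiction on study status.
- *Sites do not decide on restart.* This stands. The VSLC takes the final decision, so the conflict concerns the criterion for the request and for the committee.
- *Endpoint harm.* A reader might infer that the resistance and AE-discontinuation results depend on which section a site followed. The documents do not support this. Section 7.1.4.3 sends the suspected-failure sample for resistance testing, and that sample precedes confirmation and any decision to stop or continue. Leaving at Month 12 or stopping for CVF is not a discontinuation due to an AE.

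**Conclusion.** The contradictions are in the current protocol text and no reading satisfies each set, so they need correcting. The first is the widest: it can reach every patient who completes Month 12 before the regimen is on the market, with 135 as a ceiling rather than an estimate. The second reaches any confirmed failure. The third is narrow: it needs baseline ALT of at least 2×ULN and an ALT of 3 to below 5×ULN when restart is considered. It would be wrong to read it as covering everyone in that ALT band. This bound assumes that baseline means the participant's value before study drug.

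The effect is on drug exposure, LTFU entry, completer status and the length of safety and virology observation. The primary endpoint, survey change at Month 12 (Section 9.4.1), is not affected: Section 1.5 collects no patient questionnaires, visit-length data or patient interviews after Month 12.

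**What to change.** The sponsor's clinical team should reconcile three sets of passages and state each rule once, with cross-references elsewhere:

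1. The Month 12 exit sentence in Section 1.3 with the continuation text in Sections 1.3, 1.5, 6.1 and 6.7 and with Sections 4.4.1 and 7, saying explicitly whether a Month 12 completer who stops injections enters LTFU and how that patient is classified.
2. Section 7.1.4.3 with itself, on treatment and on study status, and with the HAART timing in Section 1.3.
3. The ALT limit in Section 10.3.3 and Table 14 with that in Section 10.6.2.

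Which rule applies in each case is a clinical decision that this review does not make. The cost is wording in the next amendment and a clarification letter to sites.
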